### 3.3.2 Concomitant Medications

3.3.2.1 Growth factor(s): Growth factors that support platelet or white cell number or function must not have been administered within the 7 days prior to enrollment (14 days if pegfilgrastim).

3.3.2.2 Corticosteroids: Patients requiring corticosteroids who have not been on a stable or decreasing dose of corticosteroid for the 7 days prior to

enrollment are not eligible. If used to modify immune adverse events related to prior therapy,  $\geq 14$  days must have elapsed since last dose of corticosteroid.

- 3.3.2.3 Previous treatment with XL184 (cabozantinib) or another MET/HGF inhibitor (tivantinib, crizotinib).
- 3.3.2.4 Investigational Drugs: Patients who are currently receiving another investigational drug are not eligible.
- 3.3.2.5 Anti-cancer Agents: Patients who are currently receiving other anti-cancer agents are not eligible.
- 3.3.2.6 Anti-GVHD or agents to prevent organ rejection post-transplant: Patients who are receiving cyclosporine, tacrolimus or other agents to prevent either graft-versus-host disease post bone marrow transplant or organ rejection post-transplant are not eligible for this trial.
- 3.3.2.7 CYP3A4 active agents: Patients must not be receiving any of the following potent CYP3A4 inducers or inhibitors: erythromycin, clarithromycin, ketoconazole, azithromycin, itraconazole, grapefruit juice or St. John's wort. A list of other known CYP3A4 inducers and inhibitors that should be discontinued prior to initiation of protocol therapy and should be avoided during study therapy if reasonable alternatives exist is included in [Appendix II](#).
- 3.3.2.8 Concomitant anticoagulation with oral anticoagulants (e.g., warfarin, direct thrombin, and Factor Xa inhibitors) or platelet inhibitors (e.g., clopidogrel) are prohibited.

Note: Low-dose aspirin for cardioprotection (per local applicable guidelines) and low dose, low molecular weight heparins (LMWH) are permitted. Anticoagulation with therapeutic doses of LMWH is allowed in subjects without radiographic evidence of brain metastasis, who are on a stable dose of LMWH for at least 6 weeks before first dose of study treatment, and who have had no complications from a thromboembolic event or the anticoagulation regimen.

- 3.3.2.9 Enzyme-inducing Anticonvulsants: Patients must not have received enzyme-inducing anticonvulsants within 14 days prior to enrollment (See [Appendix VII](#) for a list of unacceptable enzyme inducing anticonvulsants).
  - 3.3.2.10 QTc Agents: Patients who are receiving drugs that prolong QTc are not eligible (See [Appendix VIII](#) for a list of drugs that prolong QTc).
- 3.3.3 Patients who are unable to swallow intact tablets are not eligible.
  - 3.3.4 Patients who have an uncontrolled infection are not eligible.

- 3.3.5 Patients who in the opinion of the investigator may not be able to comply with the safety monitoring requirements of the study are not eligible.
- 3.3.6 Patients with active bleeding are not eligible. Specifically, no clinically significant GI bleeding, GI perforation, intra-abdominal abscess or fistula for 6 months prior to enrollment, no hemoptysis or other signs of pulmonary hemorrhage for 3 months prior to enrollment. Patients with evidence of an acute intracranial or intratumoral hemorrhage on CT or MRI are not eligible (patients with evidence of resolving hemorrhage will be eligible). In patients with CNS tumors, an MRI with ECHO gradient sequences would be required to exclude presence of petechial hemorrhages.
- 3.3.7 Patients who have had or are planning to have the following invasive procedures are not eligible:
- Major surgical procedure, laparoscopic procedure, or open biopsy within 28 days prior to enrollment.
  - Central line placement or subcutaneous port placement is not considered major surgery but must be placed at least 3 days prior to enrollment for external lines (e.g., Hickman or Broviac catheter, peripherally inserted central catheter (PICC)) and at least 7 days prior to enrollment for a subcutaneous port.
  - Core biopsy within 7 days prior to enrollment.
  - Fine needle aspirate within 7 days prior to enrollment.
  - Surgical or other wounds must be adequately healed prior to enrollment
- NOTE: For purposes of this study, bone marrow aspirate and biopsy are not considered surgical procedures and therefore are permitted within 14 days prior to start of protocol therapy.
- 3.3.8 Patients who have had significant traumatic injury within 28 days prior to enrollment are not eligible.
- 3.3.9 Patients with any medical or surgical conditions that would interfere with gastrointestinal absorption of the study drug are not eligible.

#### 3.4 Regulatory

- 3.4.1 All patients and/or their parents or legal guardians must sign a written informed consent.
- 3.4.2 All institutional, FDA, and NCI requirements for human studies must be met.

## 4.0 TREATMENT PROGRAM

Timing of protocol therapy administration, response assessment studies, and surgical interventions are based on schedules derived from the experimental design or on established standards of care. Minor unavoidable departures (up to 72 hours) from protocol directed therapy and/or disease evaluations (and up to 1 week for surgery) for valid clinical, patient and family logistical, or facility, procedure and/or anesthesia scheduling issues are acceptable (except where explicitly prohibited within the protocol).

### 4.1 Overview of Treatment Plan

Open label two-stage single arm study, with XL184 administered at 40 mg/m^2/day (cumulative weekly dose of 280 mg/m^2) on a continuous dosing schedule (one cycle = 28 days). Based on patients' BSA, there may be days that the dose will not be administered. The weekly dosing schedule can be found in [Appendix IV](#). Dosing will be performed based on body surface area (BSA), and rounded to the nearest 20 mg using a dosing nomogram (see [Appendix IV](#)). Treatment will continue until tumor progression or unacceptable toxicity.

#### 4.1.1 Dose Reduction

Dose reductions will be allowed for toxicities as outlined in [Section 5.0](#) for patients who recover to eligibility criteria as outlined in [Section 3.2](#) within 21 days of drug interruption.

#### 4.1.2 Dose Escalation

There will be no drug dose escalation.

#### 4.1.3 Criteria for Starting Subsequent Cycles

A cycle may be repeated every 28 days if the patient has at least stable disease and has again met laboratory parameters as defined in the eligibility section, [Section 3.2.7](#) and has not experienced study-drug related adverse events warranting permanent discontinuation.

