## 2.6 Overview of Proposed Pediatric Phase 2 Trial

This will be an open label two-stage phase 2 trial in the following solid tumor strata: Ewing sarcoma, rhabdomyosarcoma, non-rhabdomyosarcoma soft tissue sarcomas (NRSTS), osteosarcoma, Wilms tumor (non-statistical cohort) and other rare solid tumors (non-statistical cohort). The XL184 dose for this trial will be 40 mg/m^2/day (cumulative weekly dose of 280 mg/m^2 using a dosing nomogram), the recommended phase 2 dose determined from ADVL1211. XL184 will be administered orally once daily (20 and 60 mg tablets) on a continuous dosing schedule for cycles of 28 days with no rest period between cycles. Dosing will be performed based on body surface area (BSA), and rounded to the nearest 20 mg using a dosing nomogram as used in ADVL1211. Treatment will continue until tumor progression or unacceptable toxicity.

The primary endpoint for all non-osteosarcoma disease strata will be the objective response rate. In each of the statistical cohorts, 13 patients will be enrolled on the first stage. If at least 1 response is noted, the study will proceed to the second stage where up to an

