### 3.2.7 Organ Function Requirements

- 3.2.7.1 Adequate Bone Marrow Function Defined As:
- 3.2.7.1.1 For patients with solid tumors without bone marrow involvement:
- Peripheral absolute neutrophil count (ANC)  $\geq 1000/\mu\text{L}$
  - Platelet count  $\geq 100,000/\mu\text{L}$  (transfusion independent, defined as not receiving platelet transfusions within a

7 day period prior to enrollment)

- Hemoglobin  $\geq$  8.0 g/dL (may receive RBC transfusions).

3.2.7.1.2 For patients with solid tumors and known bone marrow metastatic disease:

- Peripheral absolute neutrophil count (ANC)  $\geq$  750/ $\mu$ L
- Platelet count  $\geq$  50,000/ $\mu$ L
- Hemoglobin  $\geq$  8.0 g/dL

Transfusions are permitted to meet both the platelet and hemoglobin criteria. Patients must not be known to be refractory to red blood cell or platelet transfusions.

3.2.7.2 Adequate Renal Function Defined As:

- Creatinine clearance or radioisotope GFR  $\geq$  70 mL/min/1.73 m^2 **or** a serum creatinine based on age/gender as follows:

Age	Maximum Serum Creatinine (mg/dL)	
	Male	Female
2 to < 6 years	0.8	0.8
6 to < 10 years	1	1
10 to < 13 years	1.2	1.2
13 to < 16 years	1.5	1.4
$\geq$ 16 years	1.7	1.4

The threshold creatinine values in this Table were derived from the Schwartz formula for estimating GFR (Schwartz et al. J. Peds, 106:522, 1985) utilizing child length and stature data published by the CDC.

- Urine protein:  $\leq$  30 mg/dl in urinalysis or  $\leq$  1+ on dipstick, unless quantitative protein is < 1000 mg in a 24 h urine sample

3.2.7.3 Adequate Liver Function Defined As:

- Total bilirubin  $\leq$  1.5 x upper limit of normal (ULN) for age
- SGPT (ALT)  $\leq$  135 U/L (3x ULN) (for the purpose of this study, the ULN for SGPT is 45 U/L)
- Serum albumin  $\geq$  2.8 g/dL.

3.2.7.4 Adequate Cardiac Function Defined As:

- No history of congenital prolonged QTc syndrome, NYHA Class III or IV congestive heart failure (CHF).
- No clinically significant cardiac arrhythmias, stroke or myocardial infarction within 6 months prior to enrollment.
- QTc  $\leq$  480 msec. Note: Patients with Grade 1 prolonged QTc (450- 480 msec) at the time of study enrollment should have correctable causes of prolonged QTc addressed if possible (i.e., electrolytes, medications).

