### 3.2.7.6 Adequate Blood Pressure Control defined as:

A blood pressure (BP)  $\leq$  the 95th percentile for age, height, and gender for pediatric patients < 18 years old ([Appendix V](#)) and  $\leq$  140/90 mmHg for patients  $\geq$  18 years old. BP should be measured as described in [Section 5.5](#), and patients should not be receiving medication for treatment of hypertension (except patients with Wilms tumor and RCC who may be eligible if on stable doses of no more than one anti-hypertensive medication with a baseline BP  $\leq$  ULN for pediatric patients and  $\leq$  140/90 for adult patients). Please note that 3 serial blood pressures should be obtained and averaged to determine baseline BP.

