**4.2 Cycle 1**

4.2.1 Therapy Delivery Map – Cycle 1 This Therapy Delivery Map (TDM) relates to Cycle 1. Each cycle lasts 28 days.	_____
	Patient COG ID number
	DOB

Criteria to start each cycle are listed in [Section 3.2.7](#). Extensive treatment details are in [Section 4.2.3](#). This TDM is on 1 page.

DRUG	ROUTE	DOSAGE	DAYS	IMPORTANT NOTES
XL184 (cabozantinib)	PO	40 mg/m  /day	1-28	See Appendix IV for dosing nomogram. The cumulative weekly dose is 280 mg/m  . XL184 should be taken at approximately the same time each day on an empty stomach; patients should fast 2 hours before and 1 hour after taking the drug.

Ht \_\_\_\_\_ cm      Wt \_\_\_\_\_ kg      BSA \_\_\_\_\_ m^2

Date Due	Date Given	Day	XL184 _____ mg	Studies
			Enter calculated dose above and actual dose administered below	
		1	_____ mg	a-n
		2	_____ mg	
		3	_____ mg	
		4	_____ mg	
		5	_____ mg	
		6	_____ mg	
		7	_____ mg	
		8	_____ mg	a
		9	_____ mg	
		10	_____ mg	
		11	_____ mg	
		12	_____ mg	
		13	_____ mg	
		14	_____ mg	
		15	_____ mg	a, c, d, k
		16	_____ mg	
		17	_____ mg	
		18	_____ mg	
		19	_____ mg	
		20	_____ mg	
		21	_____ mg	
		22	_____ mg	a, m
		23	_____ mg	
		24	_____ mg	
		25	_____ mg	
		26	_____ mg	
		27	_____ mg	
		28	_____ mg	g, i, k

See [Section 5.0](#) for Dose Modifications for Toxicities and the COG Member website for Supportive Care Guidelines.

#### 4.2.2 Required Observations in Cycle 1

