#### 5.4 Dose Modifications for Proteinuria

Proteinuria has been reported with XL184 in adult studies and pediatric trial ADVL1211.

[figure not shown]
- If urinalysis shows  $\geq$  trace protein then obtain UPC.
- If the urine protein/creatinine (P/C) ratio  $\leq 1.9$  continue XL184. If patient has Grade 3 proteinuria (urine protein/creatinine (P/C) ratio  $> 1.9$ ), a second measurement should be obtained within 72 hours. A second confirmation of Grade 3 proteinuria will be considered a DLT.
- If the second measurement confirms Grade 3 proteinuria (urine protein/creatinine (P/C) ratio  $> 1.9$ ), then interrupt XL184 treatment and re-assess weekly.
- If XL184 is held for  $\geq 21$  days then remove from protocol therapy. If the urine protein/creatinine (P/C) ratio decreases to  $\leq 1.9$  in  $< 21$  days then resume XL184 at a lower dose as outlined in [Section 5.11](#).
- Monitor the UPC weekly for 2 consecutive weeks once protocol therapy resumes.

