**Arm 3 of algorithm:**

- If BP is 11 to 25 mm Hg above the ULN on  $\geq 2$  of 3 measurements or  $> 35$  mmHg above baseline on  $\geq 2$  of 3 measurements, start anti-hypertensive therapy, continue XL184 at the same dose, and monitor BP at least twice weekly.
  - If the BP returns to  $\leq$  ULN within 14 days, continue XL184 at the same dose and continue anti-hypertensive therapy.
  - If the BP remains elevated  $\leq 25$  mm Hg above the ULN or  $> 35$  mm Hg above baseline for more than 14 days after the institution of anti-hypertensive therapy, **hold** XL184, monitor BP at least every 3 days, and follow Arm 4 of the algorithm from the point that XL184 is held. The antihypertensive therapy should be continued until the BP is less than the ULN.
    - If the BP returns to  $\leq$  ULN within 14 days, restart XL184 at a reduced dose (see [Section 5.11](#)).
    - If the BP remains  $>$  ULN for more than 14 days, patient is Off Protocol Therapy.
  - If the BP increases to  $> 25$  mm Hg above the ULN despite anti-hypertensive therapy, **hold** XL184, but continue the anti-hypertensive agent(s). Monitor the BP as clinically indicated and follow Arm 4 of the algorithm from the point that XL184 is held.
    - If the BP is  $\leq$  ULN within 14 days, XL184 may be restarted at a reduced dose (see [Section 5.11](#)).
    - If the BP is  $>$  ULN for  $> 14$  days, the patient is Off Protocol Therapy.

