### 5.7 Dose Modifications for Liver Toxicity

XL184 should be held for Grade 3 elevation of ALT, AST or bilirubin. Note: For the purposes of this trial the ULN for ALT is defined as 45 U/L regardless of the patient's baseline, and the ULN for AST is defined as 50 U/L. XL184 may be re-administered at the same dose if levels of ALT, AST and bilirubin meet eligibility criteria or baseline within 7 days of drug discontinuation. Elevated laboratory parameters should be checked at least twice weekly until eligibility criteria are met.

If lab values do not resolve to initial eligibility criteria or baseline within 7 days of interruption or if toxicity recurs with re-challenge, then this will be considered dose-limiting per [Section 5.1.1](#). The XL184 will be reduced according to [Section 5.11](#) when eligibility criteria are met.

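### The rule for starting a new cycle points back to the Section 3.2.7 entry criteria with two different scopes, and each scope conflicts with Section 5: one on antihypertensives, both on urine protein

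*Combined protocol and SAP*

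**What the plan says.** **Cycle start, narrow wording.** Section 4.1.3 lets a cycle be repeated if the patient has at least stable disease and "has again met laboratory parameters as defined in the eligibility section", 3.2.7. The opening sentences of 4.2.3, 4.3.3 and 4.4.3 carry the same limit to laboratory items.

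**Cycle start, wide wording.** The Delivery Maps in 4.2.1, 4.3.1 and 4.4.1 say "Criteria to start each cycle are listed in" Section 3.2.7, without that limit. The last lines of 4.2.3, 4.3.3 and 4.4.3 put the next cycle on Day 29, or later if the 3.2.7 conditions are not yet met.

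**Entry criteria.** Under 3.2.7.6, "patients should not be receiving medication for treatment of hypertension". Wilms tumor and renal cell carcinoma patients are excepted if blood pressure is within limits on a single agent at a stable dose. Under 3.2.7.2, urine protein may not exceed 30 mg/dl or 1+, "unless quantitative protein is < 1000 mg in a 24 h urine sample". Under 3.2.7.7, INR may not exceed 1.5.

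**On-treatment rules.** Section 5.5 Arm 2 starts antihypertensive therapy if pressure is still above the upper limit of normal (ULN) on recheck, and passes the patient to Arm 3. Arm 3 starts it at 11 to 25 mm Hg above the ULN. If pressure normalises within 14 days, Arm 3 says to "continue XL184 at the same dose and continue anti-hypertensive therapy". Section 5.4 covers a urine protein/creatinine ratio (UPC) of 1.9 or less with "continue XL184. If patient has Grade 3 proteinuria", Grade 3 being a ratio above 1.9. After a hold, it resumes XL184 at a lower dose once the ratio is back to 1.9 or less in under 21 days.

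**Dose reduction.** Section 4.1.1 allows it for patients who recover to Section 3.2 eligibility within 21 days of interruption.

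**The concern.** Section 3.2.7 was written to decide who may enter. Used again at each cycle start, it meets patients whose blood pressure or urine protein has changed on the drug, and Section 5 has its own rules for them. Neither place says which rule governs. Two sites could therefore treat the same patient differently on Day 29, each following operative text.

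Section 2.6 describes "cycles of 28 days with no rest period between cycles", so any wait at a cycle boundary is a break in intended exposure. Scans are scheduled by cycle (end of Cycle 2, before Cycles 5 and 7), so a delayed cycle also moves the response assessments. The strata are small: 13 plus 7 patients in the response-rate design and 19 plus 10 in osteosarcoma. Differences between sites in exposure and assessment timing would be hard to separate from drug effect.

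**Working it through.** This is a comparison of texts. The plan states no figure to reproduce. One side calculation tests the urine protein conflict.

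**1. Scope of the rule.** Sections 4.2.3, 4.3.3 and 4.4.3 each hold both wordings: laboratory items of 3.2.7 at the start, 3.2.7 without limit at the end. Blood pressure and antihypertensive use are not laboratory items, so the two wordings can give different answers.

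**2. Blood pressure.** Take a patient with Ewing sarcoma, rhabdomyosarcoma, other soft tissue sarcoma or osteosarcoma whose pressure rises to 11 to 25 mm Hg above the ULN and normalises on treatment within 14 days.
- Section 5.5 Arm 3: continue XL184 at the same dose and continue the antihypertensive.
- Delivery Map and closing line: 3.2.7.6 is not met while that therapy continues, so the next cycle does not start.
- Section 4.1.3: the matter does not arise, because this is not a laboratory item.

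A Wilms tumor or renal cell carcinoma patient on one agent at a stable dose can pass 3.2.7.6. On more than one agent, which the notes to the 5.5 algorithm allow, that patient cannot.

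**3. Urine protein.** Urinalysis is a laboratory item, so this conflict exists under either wording. Section 3.2.7.2 has no UPC threshold, so the question is whether UPC of 1.9 or less can go with 24 h protein of 1000 mg or more.

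24 h protein (mg) = UPC (mg/mg) × creatinine excretion (mg/day)

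The documents do not give creatinine excretion. It is assumed here to be 200 to 1500 mg/day.

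| Creatinine, mg/day (assumed) | 24 h protein at UPC 1.9 | UPC at which 1000 mg is reached |
|---|---|---|
| 200 | 380 mg | 5.0 |
| 400 | 760 mg | 2.5 |
| 1000 | 1900 mg | 1.0 |
| 1500 | 2850 mg | 0.67 |

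The break-even is 1000 / 1.9 = 526 mg/day. At an assumed 15 to 20 mg/kg/day this is a body weight of 526 / 20 = 26 kg to 526 / 15 = 35 kg. Below it, a patient with UPC of 1.9 or less passes through the 24 h exemption. Above it, part of the range up to 1.9 fails: at 1000 mg/day, UPC from 1.0 to 1.9. A patient in that range who is also above the urinalysis or dipstick limit is told by 5.4 to continue or resume, and does not meet the cycle-start rule.

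**4. Dose reduction.** Section 5.4 resumes at UPC of 1.9 or less. Section 5.5 Arms 3 and 4 restart at a reduced dose when pressure is at or below the ULN within 14 days, without requiring that antihypertensives be stopped. Section 4.1.1 asks for recovery to all of Section 3.2, which contains 3.2.7.2 and 3.2.7.6. A patient can meet the restart conditions of 5.4 or 5.5 and not those of 4.1.1.

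**5. INR (minor).** INR is a laboratory item in 3.2.7.7. It is listed for Cycle 1 in 4.2.2 but not in the later lists in 4.3.2 and 4.4.2. Sites may order further tests, but the scheduled ones do not cover the rule.

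**The case against.** The best defence is that Section 4.1.3 and the opening of each treatment-details section limit the rule to laboratory items. The Maps are one-page summaries that send the reader to those sections for detail. Section 3.2.7.6 is framed around baseline blood pressure, which 5.5 defines as the pressure at the enrollment examination, so it reads as an entry criterion, with 5.5 as the specific on-treatment rule. That may well be the intent, and the blood pressure conflict does not follow from 4.1.3. It follows from the Maps and from the closing lines, which stand in the treatment-details sections themselves. No sentence says that 5.5 prevails. The narrower reading also leaves the urine protein conflict in place.

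A reader might infer three stronger points, which the documents do not support.
- **That affected patients are removed from therapy, through Section 8.1(f).** The cycle start is postponed until the criteria are met; missing them is not in itself a reason for removal. Section 8.1(f) most naturally means the pre-treatment recheck in the Section 3.2 preamble, and its exemption from follow-up fits patients who never started.
- **That blood counts and ALT show the same contradiction.** Section 5.7 says "XL184 should be held for Grade 3 elevation of ALT, AST or bilirubin", while 3.2.7.3 sets 135 U/L, so a Grade 2 value of 136 to 225 U/L is tolerated mid-cycle and delays the next cycle. A cycle-start limit stricter than a mid-cycle hold limit is a design choice, and 5.1.2 foresees delays between cycles from myelosuppression.
- **That a loss of power can be calculated.** This would need the share of patients who lose a response because a cycle was not started. The documents give no such share.

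**Conclusion.** The point holds in limited form. The cycle-start rule has two scopes. On the wider one, patients outside the Wilms tumor and renal cell carcinoma exception who follow 5.5 do not meet the criteria while on antihypertensives. On either one, some patients whom 5.4 keeps on treatment do not meet the urine protein limit. Section 4.1.1 adds a third, different condition for restarting at a reduced dose.

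How often this would happen cannot be derived. The adverse event list in Section 6.1 puts hypertension above 20% of 3219 patients, but that is not the share on antihypertensives at Day 29. Section 2.4.1 names hypertension and proteinuria among the Cycle 1 dose-limiting toxicities and the most frequent events of the pediatric phase 1 trial, without counts. The situations are therefore foreseeable, but their frequency is unknown.

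The blood pressure and scope findings rest on the text alone. The statement that some but not all patients fail on urine protein rests on the assumed creatinine range.

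**What to change.** Reconcile 4.1.1, 4.1.3, the three Delivery Maps and 4.2.3, 4.3.3 and 4.4.3 with 5.4 and 5.5:
- use one scope for the cycle-start rule throughout;
- state which parts of 3.2.7 apply at cycle start, including whether INR is one of them;
- state whether Section 5 or 3.2.7 governs antihypertensive use and urine protein after Cycle 1;
- align 4.1.1 with the restart conditions in 5.4 and 5.5.

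The sponsor decides which rule stands; no threshold or start list is proposed here. Section 8.1(f) needs no change for this purpose. The cost is an amendment to the protocol wording and a notice to sites, with no added patients. No test need be added unless the sponsor keeps INR as a start criterion and wants it scheduled.
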